7.1 DISCONTINUATION OF STUDY INTERVENTION/EXPERIMENTAL MANIPULATION

CBT or CBT+CCT will be stopped in the event of any of the following:

- Suicidal thoughts with specific plans and intentions (Endorse item 4 or 5 on the C-SSRS and the judgment of the clinician that risk of suicide is high and imminent)
- Suicide behaviors during the study period (assessed by C-SSRS)
- Hospitalization required for any psychiatric symptoms
- Symptom worsening: > 25% increased PARS score (referenced to baseline) for more than 2 assessments in 1 week

Reasons for discontinuation will be documented, and all outcome assessments will proceed as scheduled, if possible.

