1.3 SCHEDULE OF ACTIVITIES

The following assessments and study activities may be done at each time point. For NIH Toolbox and PARS assessments, some variability in administration may occur based on subject's schedule. All assessments completed as part of [name] study *Dimensional Brain Behavior Predictors of CBT Outcomes in Pediatric Anxiety (HUM00118950)* will not be repeated for this protocol and previously collected data will be used. At P.I. discretion, participants may also not be required to complete an fMRI.

CBT-Only Timeline of Events (Primary Arm, [name] HUM00118950)

CBT+CCT Timeline of Events (Primary Arm, [name] HUM00169730)

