6.1.2 ADMINISTRATION AND/OR DOSING

Cognitive behavioral therapy: CBT treatment will be delivered over the course of up to 12 weeks including 60 minutes of face-to-face meeting at the clinical setting. CBT may be delivered via remote video conference if social distancing policies prohibit this type of in-person interaction (e.g., COVID-19). If a remote video conference is not possible, therapy sessions may be scheduled as in-clinic remote visits in the Rachel Upjohn Building.

Computerized cognitive training: The CCT intervention will consist of ~30 minutes of CCT games that may be completed prior to CBT sessions 4-12, to engage cognitive control capacity prior to receipt of CBT. These sessions of CCT may be completed at home if social distancing policies prohibit this type of in-person study activity (e.g., COVID-19). Participants may also receive up to four weeks of at home CCT

(~30 min/day), 5 days per week, for up to two weeks prior to beginning CBT and up to 4 weeks after beginning the 12-week CBT protocol. Participants may complete CCT on an iPad provided by Akili Interactive, or they may complete CCT by downloading the application onto their own Akili-compatible personal device.

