6.4 STUDY INTERVENTION/EXPERIMENTAL MANIPULATION ADHERENCE

Assessments (or subsets of questions from these measures) will mainly be completed as part of the parent study and utilized for analysis in this protocol. At each time point, assessments may include:

Assessments Completed by Independent Evaluator– Weeks 0, 1, 3, 6, 9 & 12

- a) PARS
- b) Clinical Global Impressions-Severity and Improvement Scale (CGI); (*Guy and Bonato 1970*).

Assessments by Clinician – Weeks 1-12

- a) CGI (S/I)
- b) Treatment Adherence Rating Scale (TARS) A therapist-administered instrument to assess patient completion of assigned CBT or RMT homework.
- c) C-SSRS (since last visit)
- d) CGAS

Assessments Completed by Subjects – Weeks 1-12

- a) Medication Adherence (also all fMRIs)
- b) MASC – week 1, 3, 6, 9, 12
- c) CDI – week 1, 3, 6, 9, 12
- d) CGI-I (parent report) – week 3, 6, 9, 12.
- e) FAS (parent report) – week 12
- f) BDI (parent report) – week 12
- g) BAI (parent report) – week 12
- h) Beverage and Food Questionnaire – week 3 and 12
- i) GRIT Scale – week 12
- j) SCARED (parent) – week 1, 3, 6, 9, 12
- k) SCARED (child) – week 1, 3, 6, 9, 12
- l) Life Events Checklist – week 12

Other Assessments

- a) CGAS (Independent Evaluator, Week 0 and 12)
- b) Credibility/Expectancy Questionnaire (CEQ; Subject, week 3) – A 6-item scale rating the patient's expectations for treatment success (Devilly & Borkovec, 2000)
- c) Working Alliance Inventory (WAI; Subject, Weeks 6 & 12) – A 12-item scale rating the patient's feelings about their relationship with the therapist (Horvath & Greenberg, 1989) – approximately 5 minutes.
- d) Randomization “guess” form to be completed by Independent Evaluator at week 12 to assess blinding (CBT-only).
- e) Self-Assessment Manikin (SAM; Subject, may be completed before and after each session of CCT) – A 3-item scale rating the patient's feelings of pleasure, arousal, and dominance (Bradley & Lang, 1994) – approximately 2 minutes.
- f) Behavior Rating Inventory of Executive Function, Second Edition (BRIEF2; Parent, pre-RMT course of treatment, pre- and post-CBT course of treatment as well as week 3 of CBT, and when completing fMRI after completion of 4 weeks at home CCT for the CBT+CCT group) – at 63-item parent-report scale assessing executive function of the patient (Gioia, Isquith, Guy, & Kenworthy, 2015) – approximately 10-15 minutes.

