8.2 SAFETY ASSESSMENTS

- **fMRI Safety Screen form** in order to ensure that there are no contraindications for fMRI. This form is provided by the fMRI lab and is not included within study documentation. The most current version of this screening form will be used at all times to ensure the safety of participants undergoing fMRI.
- **Columbia Suicide Severity Rating Scale**, present/lifetime version (Posner, Oquendo et al. 2007). A clinician-rated scale assessing suicidal ideation and behavior.
- **Pediatric Anxiety Rating Scale (PARS)**. A clinician-administered assessment to rate the severity of anxiety symptoms associated with common DSM-V anxiety disorders (social phobia, separation anxiety disorder, and generalized anxiety disorder) in children. Total scores on this scale range from 0 to 30, with scores above 13 indicating clinically meaningful anxiety. Approximately 20–30 minutes. Symptom worsening: > 25% increased PARS score (referenced to baseline) for more than 2 assessments in 1 week

Any safety-related assessments (C-SSRS administered through the parent study, fMRI screening) or primary outcome measure (PARS– independent assessor may administer at weeks 0, 1, 3, 6, 9, and 12; missed week 9 will not be reported as a deviation) that are missed for a study visit/week of therapy a participant completed will be reported to the IRB as a protocol deviation. For the independent assessments, we will accept a window of \pm 1 week. For CBT+CCT group, the 3-week, 6-week, and 9-week PARS assessments are completed under this protocol only, and a PARS assessment may be completed under this protocol prior to beginning at-home CCT treatment if there have been more than about 6 weeks since the RMT week 12 PARS. For the CBT-only group, the 3-week PARS assessment is completed under this protocol only. However, for the other assessments, missing or late assessments will not be reported as protocol deviations unless they constitute > 10% of the total assessments. In order to accommodate inevitable scheduling conflicts, holidays, etc., participants will be allowed to miss up to 4 sessions of therapy, and the sessions must be completed within 16 weeks. These allowances should affect neither the scientific integrity nor the safety monitoring provisions of the protocol.

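### The PARS symptom-worsening stop needs at least 3 raised scores in 1 week, but the PARS visits listed after week 0 put at most 2 in any week

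*Combined protocol and SAP*

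**What the plan says.** Section 7.1 lists the events that stop CBT or CBT+CCT. One is tied to an anxiety score: "Symptom worsening: > 25% increased PARS score (referenced to baseline) for more than 2 assessments in 1 week". Section 8.2 gives the same rule in the same words.

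The PARS schedule appears twice and agrees. Section 6.4 puts the independent evaluator's PARS at "Weeks 0, 1, 3, 6, 9 & 12". Section 8.2 says the "independent assessor may administer at weeks 0, 1, 3, 6, 9, and 12; missed week 9 will not be reported as a deviation". On timing, section 8.2 states: "For the independent assessments, we will accept a window of" plus or minus 1 week.

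The clinician's weekly set in section 6.4 is CGI, TARS, C-SSRS and CGAS, without PARS. For CBT+CCT, section 8.2 adds that "a PARS assessment may be completed under this protocol prior to beginning at-home CCT treatment", if more than about 6 weeks have passed since the RMT week 12 rating. Section 6.1.2 allows at-home CCT "for up to two weeks prior to beginning CBT and up to 4 weeks after beginning the 12-week CBT protocol".

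**The concern.** The rule and the visit schedule do not fit together. The rule asks for several raised ratings within one week, while the ratings are spaced 2 to 3 weeks apart. Staff who follow the protocol exactly would not collect the scores needed to apply it.

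The protocol treats PARS as a safety measure. It sits among the safety assessments, and a missed rating other than week 9 is reported to the IRB. Section 2.3.1.1 lists worsening anxiety as a risk, and section 10.1.6 plans no regular external monitoring. If the only anxiety-score stop cannot fire from scheduled visits, a stated automatic safeguard becomes in practice a matter of discretion.

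**Working it through.** The check is a count of visits. Week k is placed on day 7k, and a week is read generously as a span in which the last rating is no more than 7 days after the first.

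**Required (sections 7.1 and 8.2).** More than 2 in 1 week means at least 3 ratings within 7 days, each above 1.25 times the reference score.

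**Available at nominal times (sections 6.4 and 8.2).** Weeks 1, 3, 6, 9 and 12 are days 7, 21, 42, 63 and 84. The gaps are 14, 21, 21 and 21 days. The smallest exceeds 7, so at most 1 rating falls in any 7 days.

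**Available with the windows.** The visits may fall on days 0–14, 14–28, 35–49, 56–70 and 77–91.

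- Two in a week is possible. Weeks 1 and 3 need a combined shift of 14 − 7 = 7 of the 14 days available, for example days 10 and 17. Later neighbours come within 21 − 14 = 7 days only at the extreme edges.
- Three in a week is not. The shortest span of three successive visits is the nominal span minus 14 days:

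| Visits (weeks) | Nominal span (days) | Shortest span with windows (days) |
|---|---|---|
| 1, 3, 6 | 42 − 7 = 35 | 35 − 14 = 21 |
| 3, 6, 9 | 63 − 21 = 42 | 42 − 14 = 28 |
| 6, 9, 12 | 84 − 42 = 42 | 42 − 14 = 28 |

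The smallest is 21 days against the 7 required. With a window of w days, three visits would fit only if 35 − 2w ≤ 7, that is w ≥ 14, twice the window allowed.

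**Adding week 0.** Where week 0 is the reference, it cannot be 25% above itself. If an older score is the reference, weeks 0 and 1 (days 0 and 7) give 2 ratings in 7 days at nominal times. A third from the listed visits requires week 0 on day 7 and week 3 on day 14, both at the window limits, with week 1 between them.

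**Adding the optional pre-CCT rating.** If it is separate from week 0 and is also counted, three ratings can fall close together near the start. Days −1, 0 and 6, for example, span 7 days. This counts scores taken before or around the start of treatment as evidence of worsening during it.

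**The case against.** The strongest reply is that a rule asking for several scores in one week presumes repeat ratings for cause. Section 6.5.1 allows a clinical assessment in an urgent crisis, and section 1.3 says: "For NIH Toolbox and PARS assessments, some variability in administration may occur". Much of the assessment belongs to the parent study, and the timelines in section 1.3 could not be read in the text used here. This stands in part. Nothing visible forbids extra PARS ratings, but nothing prescribes them either, and PARS is not named as the crisis instrument. The weekly symptom monitoring in section 2.3.1.1 does not close the gap, because the weekly clinician set omits PARS. Even a PARS exactly every 7 days would put only 2 in a 7-day span.

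A reader might infer that the rule can never be met. The documents do not support that. Unscheduled ratings could meet it, and so could the start-of-treatment combinations shown above. The claim is safe only for listed visits after week 0.

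A reader might also infer that the CBT+CCT group has no usable baseline. That goes too far. Section 8.2 calls for a fresh PARS when the RMT week 12 rating is more than about 6 weeks old. The version 8.0 entry in section 10.2 explains this as obtaining an accurate measure of symptoms reasonably close to the start of at-home CCT. Together these imply that the reference is the last rating before treatment. It should be stated, but this is a clarification.

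**Conclusion.** The defect holds as stated: the rule needs 3 ratings in 7 days, and the listed visits after week 0 supply 1 nominally and 2 at most. This rests on the schedule in sections 6.4 and 8.2, on the section 1.3 timelines adding no further PARS visits, and on scores from before treatment not counting as post-baseline.

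It is minor. A reader might conclude that worsening children are left unprotected, but the protocol does not support that. The suicidality and hospitalization stops in section 7.1 remain. Section 6.5.1 requires withdrawal of a child who needs more than the limited extra help or who starts a medication that is not permitted. Sections 2.3.1.1 and 7.2 allow withdrawal on judgment, and clinicians rate weekly. No endpoint or analysis is affected.

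One side note adds no weight. Section 8.2 says of PARS: "Total scores on this scale range from 0 to 30". From a reference of 24, a rise of more than 25% requires a score above 1.25 × 24 = 30, so it is impossible from 24 upward. From 23 it requires 29 (1.25 × 23 = 28.75). The documents do not give the share of children at 24 or more.

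**What to change.** In sections 7.1 and 8.2, replace the three-in-a-week condition with one the schedule can meet, such as *PARS more than 25% above the reference at 2 consecutive completed post-baseline PARS assessments*. The word *completed* matters because the ratings are optional in wording and a missed week 9 is excused. State that the reference is the last PARS before at-home CCT or CBT begins, whichever comes first. The clinical team should confirm both the count of 2 and the 25%.

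This is a wording change in two places and needs no new data. Its costs are:

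- **Slower confirmation.** A within-week rule becomes one confirmed at the next visit. The wait is 2 weeks from week 1 to week 3 (0 to 4 with windows), 3 weeks between later visits (1 to 5), and 6 weeks from week 6 to week 12 if week 9 is missed (4 to 8). A first rise at week 9 is confirmed only at week 12, and a first rise at week 12 cannot be confirmed. Judgment-based withdrawal under sections 2.3.1.1 and 7.2 must cover these gaps.
- **Some early stops.** Probably only a few children would be affected, but the plan gives no rate of worsening from which to calculate the number. A stop at week 3 or 6 comes after about 3 or 6 weekly sessions, below the 8 required in section 4.3. It could reduce the 14 usable CBT+CCT participants expected in section 5. Section 7.1 continues outcome assessments where possible. Section 7.2 replaces treated children who are discontinued from the study, but a treatment stop under 7.1 need not be a study discontinuation, so the text should say whether replacement applies.

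An alternative closer to the within-week intent is to prescribe repeat PARS ratings within a week of a raised score. That confirms sooner but adds visits.

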- 11) Obsessive-Compulsive Inventory (OCI) (Foa, Huppert et al. 2002). An 18-item self-report scale for OC behavior, from normal to pathological. Total scores on this scale range from 0 to 72, with scores above 21 indicating a likely OCD diagnosis. Approximately 10 minutes.
- 12) Multidimensional Anxiety Scale for Children (MASC); (March, Parker et al. 1997). Self-report assessing anxiety. Approximately 10-15 minutes.
- 13) Children's Depression Inventory (CDI); (Kovacs, 1992). Self-report, 28 item scale on depressive symptoms. Approximately 5 minutes.
- 14) Pediatric Anxiety Rating Scale (PARS). A clinician-administered assessment to rate the severity of anxiety symptoms associated with common DSM-V anxiety disorders (social phobia, separation anxiety disorder, and generalized anxiety disorder) in children. Total scores on this scale range from 0 to 30, with scores above 13 indicating clinically meaningful anxiety. Approximately 20–30 minutes.
- 15) Clinical Global Impressions-Severity and Improvement Scale (CGI-S/I); (Guy and Bonato 1970).
- 16) Children's Global Assessment Scale (CGAS); (Shaffer, Gould et al. 1983). A single-item scale, administered by the clinician.
- 17) Columbia Suicide Severity Rating Scale, present/lifetime version (Posner, Oquendo et al. 2007). A clinician-rated scale assessing suicidal ideation and behavior. Approximately 5 min.
- 18) Kiddie Schedule for Affective Disorders and Schizophrenia (K-SADS); (Kaufman, Birmaher et al., 1997). Standard assessment tool to obtain a diagnosis, may include parent interview. Approximately 3-4 hours.
- 19) Grit Scale: (Duckworth, 2007): 12 item measure. Add up all the points and divide by 12. The maximum score on this scale is 5 (extremely gritty), and the lowest scale on this scale is 1 (not at all gritty).
- 20) Life Events Checklist: Adapted from Child and Adolescent Survey of Experiences: Child Version (CASE) (Allen and Rapee, 2009). Assessing events people may find bad or upsetting, as well as events people may find good or enjoyable. Approximately 15 minutes.
- 21) Wechsler Abbreviated Scale of Intelligence (WASI). A short-form administration of two sub-tests of the WAIS (vocabulary and matrix design) to establish IQ. 15 min (can be completed at any time prior to fMRI #2).

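### With week 0 as baseline, the scheduled PARS cannot trigger the symptom-worsening stop: it needs three PARS in one week and the schedule gives at most two

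*Combined protocol and SAP*

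**What the plan says.** Section 7.1 lists four events on which CBT or CBT+CCT will be stopped. Three concern suicidal plans and intentions, suicidal behaviour, and psychiatric hospitalization. The fourth is "Symptom worsening: > 25% increased PARS score (referenced to baseline) for more than 2 assessments in 1 week". Section 8.2 repeats it under the PARS entry.

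Section 8.2 gives the schedule: the "independent assessor may administer at weeks 0, 1, 3, 6, 9, and 12". It adds "For the independent assessments, we will accept a window of" one week either side, and "missed week 9 will not be reported as a deviation". Section 6.4 gives the same six weeks for the independent evaluator, under the permissive lead-in "At each time point, assessments may include". Its separate weekly clinician list (weeks 1 to 12) holds the CGI, TARS, C-SSRS and CGAS, but not the PARS.

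On the scale, section 8.1.1 states: "Total scores on this scale range from 0 to 30, with scores above 13 indicating clinically meaningful anxiety".

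The rule does not say which PARS is the baseline. For the CBT+CCT group, section 8.2 refers to the PARS at week 12 of RMT and says that "a PARS assessment may be completed under this protocol prior to beginning at-home CCT treatment" if more than about six weeks have passed since then.

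**The concern.** The rule and the assessment schedule do not fit together. The rule counts PARS within a single week, while the schedule spaces them two to three weeks apart after week 1. A mandatory stop that planned visits cannot reach depends on someone deciding, without instruction, to add PARS assessments.

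A second, smaller difficulty is that a percentage rise on a bounded scale becomes unreachable near the top. If only the count were repaired, children who start with very high scores would still be outside the rule.

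At stake is a safety provision for children, not an estimate or a test. Section 2.3.1.1 lists worsening anxiety as a study risk, and the other three mandatory stops cover suicidality and hospitalization. A child whose anxiety worsens without either would, in practice, be handled by clinical judgement and the withdrawal conditions of section 6.5.1, not by the numeric rule.

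**Working it through.** The plan gives no figure of its own to reproduce. The check uses these inputs:

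- Rule: PARS above 1.25 × baseline at more than 2, hence at least 3, assessments in 1 week (7.1, 8.2).
- Schedule: weeks 0, 1, 3, 6, 9, 12 (6.4, 8.2).
- Window: ±1 week (8.2).
- Scale: 0 to 30 (8.1.1, 8.2).
- Assumption: week 0 is the baseline.

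**Count.** The permitted ranges in weeks are: week 0, −1 to 1; week 1, 0 to 2; week 3, 2 to 4; week 6, 5 to 7; week 9, 8 to 10; week 12, 11 to 13. The shortest span that can hold a set of visits is the largest lower limit minus the smallest upper limit, or zero if that is negative.

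| Post-baseline visits | Shortest span with windows | Span at nominal timing |
|---|---|---|
| 1, 3 | 2 − 2 = 0 weeks | 2 weeks |
| 3, 6 | 5 − 4 = 1 week | 3 weeks |
| 6, 9 | 8 − 7 = 1 week | 3 weeks |
| 9, 12 | 11 − 10 = 1 week | 3 weeks |
| 1, 3, 6 | 5 − 2 = 3 weeks (21 days) | 35 days |
| 3, 6, 9 | 8 − 4 = 4 weeks (28 days) | 42 days |
| 6, 9, 12 | 11 − 7 = 4 weeks (28 days) | 42 days |

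At most two post-baseline PARS therefore fall within 7 days, and only one at nominal timing, against three required. Even a PARS every week, done on time, would put only two within 7 days.

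**Where the baseline assumption matters.** For weeks 0, 1 and 3 the shortest span is 2 − 1 = 1 week, exactly 7 days, with week 0 done a week late and week 3 a week early. If week 0 is the baseline it cannot exceed itself, so this set does not help. If an earlier PARS were the reference, it could just meet the count.

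**Ceiling.** The rule needs a score s with s > 1.25 × b and s ≤ 30, which requires b < 24.

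| Baseline b | 1.25 × b | Lowest qualifying score | Largest possible rise, (30 − b)/b |
|---|---|---|---|
| 20 | 25.00 | 26 | 50.0% |
| 22 | 27.50 | 28 | 36.4% |
| 23 | 28.75 | 29 | 30.4% |
| 24 | 30.00 | none | 25.0% |
| 25 | 31.25 | none | 20.0% |
| 30 | 37.50 | none | 0% |

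No score qualifies from 24 to 30. Section 5 describes parent-study entry as PARS above 10 and gives no upper limit. The parent eligibility criteria are not reproduced here, and no baseline distribution is given.

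**The case against.** The strongest reply is that the rule speaks of assessments, not scheduled ones, and may be meant to imply repeat PARS in a child who is getting worse. That stands as far as it goes: a reader might infer that the stop can never operate, and the documents do not support this. Unscheduled PARS could supply the count, and section 6.5.1 allows an urgent clinical assessment. But that section does not name the PARS or any repeat frequency, and nothing else requires repeats.

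A reader might also infer that worsening children are left unprotected. They are not:

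- Three mandatory stops remain in 7.1.
- Clinicians rate the C-SSRS, CGI and CGAS weekly (6.4).
- Section 2.3.1.1 describes weekly symptom monitoring through the parent study and says that consultation on worsening may lead to withdrawal.
- Section 6.5.1 requires withdrawal when needs exceed the limited extra sessions or a non-permitted medication is started.
- Section 7.2 allows withdrawal in the participant's interest.

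On the ceiling, any percentage rule on a bounded scale has one, and no child is shown to start at 24 or more. This is fair, and the ceiling is accordingly a secondary point.

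It is tempting to close the gap at 24 and above with an automatic stop on any worse CGI rating. That would stop such children far more readily than a child at 23, who must reach 29. The documents give no CGI anchors to justify a cut-off, and sessions 6 to 12 are exposure work (6.1.1), when transient rises are plausible.

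**Conclusion.** The point holds, as a minor safety correction that should be made. With week 0 as the baseline, scheduled PARS give at most two post-baseline readings in any week against the three required, and the closest three span 21 days. The count can be met only by unscheduled PARS that the documents do not call for, or by taking an earlier baseline and using the windows at their limits. The undefined baseline is therefore part of the defect.

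Secondarily, the threshold is out of reach for any baseline from 24 to 30. The number of children affected cannot be derived from the documents, and none is claimed.

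The conclusion rests on the PARS weeks in 6.4 and 8.2, which agree; the timelines in section 1.3 could not be read in the available text. The parent protocol, under which most of these PARS are done, was not available either. No efficacy estimate or trial conclusion is affected.

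**What to change.** Put the same text in 7.1 and 8.2, for example: *Symptom worsening: a PARS total more than 25% above the reference score at two consecutive PARS assessments. The reference is the last PARS before CBT or at-home CCT begins, whichever comes first. After a first such score, a repeat PARS is done within about one week.*

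The deadline for the repeat matters. Without it, confirmation from scheduled visits would take two to three weeks nominally, and about six if week 9 is missed (12 − 6 = 6), in a course of up to 12 weeks.

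For a reference score of 24 or more, state that sustained worsening on the CGI already collected prompts the clinical consultation in section 2.3.1.1, with the cut-off set by the clinical team. Leave the suicidality and hospitalization stops as they are.

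The cost is a short amendment in two places, a few unscheduled PARS (20 to 30 minutes each by section 8.1.1), possibly a few more stops, and a check for consistency with the parent protocol. No new scheduled visit is needed. The rule will remain insensitive just below the ceiling: at 23, only scores of 29 and 30 qualify.
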